## STATEMENT OF COMPLIANCE

The trial will be carried out in accordance with International Conference on Harmonization Good Clinical Practice (ICH GCP) and the following:

- United States (US) Code of Federal Regulations (CFR) applicable to clinical studies (45 CFR Part 46, 21 CFR Part 50, 21 CFR Part 56, and 21 CFR Part 812)

National Institutes of Health (NIH)-funded investigators and clinical trial site staff who are responsible for the conduct, management, or oversight of NIH-funded clinical trials have completed Human Subjects Protection and ICH GCP Training.

The protocol, informed consent form(s), recruitment materials, and all participant materials will be submitted to the Institutional Review Board (IRB) for review and approval. Approval of both the protocol and the consent form must be obtained before any participant is enrolled. Any amendment to the protocol will require review and approval by the IRB before the changes are implemented to the study. In addition, all changes to the consent form will be IRB-approved; a determination will be made regarding whether a new consent needs to be obtained from participants who provided consent, using a previously approved consent form.

## 1 PROTOCOL SUMMARY

### 1.1 SYNOPSIS

- Title:** A Transnasal Evaporative Cooling Device for Acute Treatment of Migraine
- Study Description:** This is a prospective, double-blind, sham-controlled, randomized study to assess the safety, tolerability, and optimal dose of the COOLSTAT Transnasal Thermal Regulating Device for acute treatment of migraine. The hypothesis is that evaporative cooling induced by the CoolStat using only ambient, dry air will reduce the pain and other symptoms of migraine headaches during an acute migraine episode.
- Objectives:**
- Primary Objective:
- To evaluate the safety, tolerability and optimal dose of the CoolStat for acute treatment of migraine
- Secondary Objectives:
- To assess the efficacy of CoolStat, by way of reduction in severity of reported pain and other symptoms post treatment compared to baseline.
  - To confirm the sham and the blinding procedures
  - To determine the treatment effect size to use in future sample size calculations for a pivotal randomized trial.

**Endpoints:**

Primary Endpoints:

- Safety of the CoolStat device measured by incidence of adverse events
- Tolerability of the CoolStat device by percent of subjects who fail to complete the full treatment session.
- Pain relief at 2 hours post treatment.

Secondary Endpoints:

- Pain relief immediately post treatment and at 24 hours post treatment.
- Pain freedom immediately, 2 hours, and 24 hours post treatment.
- Relief of migraine associated symptoms (nausea/vomiting, photophobia, phonophobia) immediately, 2 hours, and 24 hours post treatment.
- Freedom from migraine associated symptoms (nausea/vomiting, photophobia, phonophobia) immediately, 2 hours, and 24 hours post treatment.
- Use of rescue medication between 2 and 24 hours.
- % of subjects who believe they received active treatment in each arm.

**Study Population:**

75 women and men diagnosed with episodic migraine who are at least 18 years of age. Up to 100 patients may be consented, but only 75 will be randomized to treatment.

**Phase:**

N/A

**Description of Sites/Facilities Enrolling Participants:**

Participants will be enrolled from up to 3 clinical sites (US only). Study sites will be headache-specific treatment centers.

**Description of Study Intervention:**

The CoolStat induces evaporative cooling by delivering dry, ambient air into one nostril and over the nasal turbinates in a unidirectional fashion before flowing freely out of the other nostril and the mouth. The nasal turbinates are highly vascularized, mucus-containing membranes with a large, convoluted surface area. As the dry air from COOLSTAT flows over the moist turbinates, it induces the liquid water (mucus) on the turbinates to change phase, from a liquid to a gas. To complete the phase change, the liquid water molecules need energy, which is drawn from the turbinate membrane tissue. This process locally extracts energy from this tissue bed, focused in the region of the turbinates. This extraction of energy causes local cooling in this area, which is believed to reduce symptoms of migraine.

[figure not shown]
**Study Duration:**

6 months

**Participant Duration:**

Up to 60 days (24 hours of study activity)

## 1.2 SCHEMA

### 1.3 SCHEDULE OF ACTIVITIES (SOA)

Procedure	Screening (Day -60 to 0)	Treatment Visit (Day 0)	Post Treatment (2 hours) ± 15 minutes	Post Treatment (24 hours) ± 2 hours
Informed consent	X			
Demographics	X			
Medical history	X			
Eligibility criteria verification	X			
Randomization		X		
Physical exam (height and weight)		X		
Vital signs (blood pressure, pulse oximetry, tympanic temperature)		X*	X	
Administer study intervention		X		
Most Bothersome Symptom		X		
Head pain severity score		X	X	X
Nausea severity score		X	X	X
Photosensitivity severity score		X	X	X
Phonosensitivity severity score		X	X	X
Concomitant medications review	X	X	X	X
Adverse event review and evaluation		X	X	X
Complete Case Report Forms (CRFs)	X	X	X	X

*\*Vitals will be taken immediately pre and post treatment session.*

## 2 INTRODUCTION

### 2.1 STUDY RATIONALE

Migraine is a severely disabling neurologic condition and is the sixth most disabling disorder worldwide, affecting over a billion people. The majority of those with migraines experience them episodically, defined as less than 15 migraine days per month. Migraine can cause a significant reduction in quality of life as well as loss of productivity. The global economic burden of migraine is staggering at approximately \$20 billion in the U.S. and \$56 billion worldwide per year.

Migraine affects significantly more women than men and is the leading cause of disability in people under fifty (Steiner, 2018). First line treatment options are medications such as triptans and NSAIDs, which are associated with adverse effects, are contraindicated in those with cardiovascular issues, and put patients at risk for medication-overuse headache. In addition, more than 50% of chronic migraineurs discontinue or change their preventive treatment drug at some point due to its lack of efficacy or tolerability (Ford, 2017). Neuromodulation therapies that target the autonomic nervous system are gaining traction due to their safety profile and relative effectiveness.

The pathophysiology of migraine is complex, not fully understood, and not within the scope of this study. There is evidence that the headache phase of migraine is caused by activation of nociceptors in the trigeminal ganglion (Puledda, 2017). The sphenopalatine ganglion (SPG), a large ganglion located behind the superior nasal turbinate, is closely associated with the trigeminal system (Robbins, 2016). Several studies have shown that intranasal SPG nerve block with lidocaine provides relief from acute migraine headaches (Maizels, 1999; Kudrow, 1995; Binfallah, 2018). Another possible mechanism is stimulation through the nasal cerebral pathway via olfactory epithelium. The COOLSTAT Transnasal Thermal Regulating Device has the potential, using a simple non-invasive transnasal evaporative cooling process, to activate these (or other) mechanisms, providing pain and symptom relief reduction in patients with migraine.

The CoolStat device uses transnasal high flow dry air to cause local cooling of the nasopharynx due to evaporation of nasal mucosal water. The device also has a feature that intermittently mists several drops of water (saline) into the nose, which is used to augment the evaporative cooling process, prevent nasal turbinate desiccation, and minimize discomfort to the patient. The overall hypothesis is that optimized transnasal cooling with the CoolStat device will reduce the intensity of migraine headaches during an acute episode. More detail can be found in the *CoolStat Investigator Brochure*.

The objectives of this study are to evaluate the safety, tolerability, and optimal dose (air flow rate) of the CoolStat to reduce pain and other symptoms associated with episodic migraine with or without aura.

### 2.2 BACKGROUND

The prevalence of migraine in the U.S. is increasing, with 15% of the population suffering from either episodic or chronic migraine. Migraine is one of the most common reasons for emergency room visits. Despite treatment recommendations, opioids are still overprescribed for migraine patients. This is especially the case in emergency departments (EDs) where one study found that opioids are prescribed at over 50% of migraine ED visits (Minen, 2014). It is apparent that this phenomenon is contributing

significantly to the growing opioid epidemic. The use of opioids in this population carries a high risk of 'medication-overuse-headache', when used more than 10 times/month, and can quickly lead to opioid dependency (Bigal, 2008). Medication overuse is also the most common reason why episodic migraine transforms into chronic migraine.

Current therapies for migraine are suboptimal, expensive and ineffective in curbing the global opioid epidemic. There is an enormous unmet need for an effective and affordable non-drug abortive therapy for acute migraine to significantly improve quality of life and substantially reduce the cost burden to our healthcare system and society.

#### Migraine prototype study:

A single-blinded, randomized trial was conducted at the Johns Hopkins Bayview Hospital headache clinic in Baltimore, MD, to study potential therapies for migraine, centered on evaporative cooling (Shah, 2021). This study evaluated the safety and efficacy of four potential therapies consisting of different air mixtures flowing in the nose and out the mouth: 1) a flow of dry oxygen, 2) a flow of dry air, 3) a flow of humidified oxygen, and 4) a flow of humidified air (control). All four gases were warmed to 37°C and delivered through a face mask (not the COOLSTAT device) with the study gases flowing in the nose and freely out of the mouth. The subjects were awake and otherwise healthy, excluding their migraine symptoms. The objective of the study was to assess safety and the ability to reduce symptoms from migraine.

Fifty-one (51) patients were enrolled in the study, of which 13 patients (mean age 49 years, 81% female) received humidified oxygen therapy and 9 patients (mean age 42 years, 82% female) received dry air therapy. Patients were randomized and blinded to their treatment group. There was significant pain relief at 2 hours post treatment compared to baseline reported by patients who received dry air, dry oxygen and humidified oxygen. Patients in the control group did not show significant pain relief from baseline to 2 hours post treatment.

A two-way ANOVA was conducted to examine the effect of gas type and moisture content in reducing headache symptoms in migraine (pain score reduction). There was a statistically significant interaction between the effects of gas type and moisture content on the headache score reduction,  $F(1,47) = 10.471$ ,  $p = 0.002$ . Simple main effects analysis showed that there were no significant differences between dry oxygen and dry air ( $p = 0.906$ ), but there were statistically significant differences between these gases when they were humidified ( $p < 0.001$ ).

No adverse events were reported in this study. It was concluded that high flow dry air is safe and appears to be effective in treating acute migraine pain and associated symptoms.

#### Neurogenic fever study:

The CoolStat is also currently being studied in a multi-center, open-label study for targeted temperature management to treat neurogenic fever in adults with ischemic or hemorrhagic stroke, seizure, or metabolic encephalopathy, under IDE G160198. The objective of this study is to evaluate safety and efficacy of the CoolStat in reducing core temperature in the study population. Results from an analysis of the first 10 subjects showed that inducing normothermia with the CoolStat device over an 8-hour period appears to be safe, feasible, and not associated with hemodynamic changes or significant shivering (Badjatia, 2020). No changes were observed in arterial or ICP while delivering transnasal cooling. This study has moved into its next phase, in which the same population is being cooled for 24

hours using the CoolStat device and preliminary results show sustained safety and efficacy during this extended cooling period.

#### Migraine dose escalation study:

A dose escalation and tolerability study was completed using the CoolStat device at the Johns Hopkins Bayview Hospital headache clinic in Baltimore, MD. 15 subjects experiencing migraine on the day of treatment were enrolled. Three air flow rates were tested and tolerability and efficacy were assessed for increasing air flow rates: 24 LPM, 36 LPM and 48 LPM. Five (5) subjects were tested at each flow rate, starting at the lowest flow rate (24 LPM). If the majority (3/5) of the subjects in the lowest flow rate group tolerated the full 10 minute treatment, the next group would receive an incrementally higher flow rate. All of the flow rates were found to be tolerable by study subjects, with 13 of the 15 subjects tolerating the full 10 minute treatment session. Although anecdotal (due to the small size of the study), there was also positive reports of reductions in migraine symptoms, which also appears to be related to flow, i.e., migraine symptoms reduced more with increased flow rates. 73% of the 15 subjects experienced pain relief immediately after treatment compared to baseline and 53% of subjects reported sustained pain relief at 2 hours post treatment. 67% of subjects reported that the benefit of the CoolStat treatment outweighed any discomfort they experienced during the treatment session and 73% said they would use the device again. 60% of subjects said the CoolStat works just as well or better than their current rescue medication. The adverse events that occurred were all graded as mild and anticipated (stuffy nose, burning sensation during treatment session) and resolved on their own. There were no serious adverse events or unanticipated device effects. This study demonstrated that the CoolStat is safe and tolerable for use in patients with acute migraine attacks.

## 2.3 RISK/BENEFIT ASSESSMENT

### 2.3.1 KNOWN POTENTIAL RISKS

Anticipated risks or adverse events (AEs) that may occur are nasal discomfort, sinus pressure, dry nose or mouth, runny nose, and epistaxis (nose bleed). There is also a minor risk to subject confidentiality.

Subjects will be advised of the potential risks and benefits associated with this study in the IRB approved ICF.

### 2.3.2 KNOWN POTENTIAL BENEFITS

This is an investigational study in which any direct benefit to participants cannot be guaranteed. There is a chance that the study treatment may provide some relief from the pain and symptoms associated with migraine.

The results from this study will provide information on using a new device, the CoolStat, in a clinical setting, for treating migraine pain and associated symptoms using only a flow of dry, ambient air. Study participants will help the medical community gain new knowledge relating to development of an effective, drug-free process and device to treat acute migraines, which could help to substantially curb the use of opioid medication and subsequent dependence issues in the migraine population.

### 2.3.3 ASSESSMENT OF POTENTIAL RISKS AND BENEFITS

The risks to subjects in this study are considered minimal. Subjects will be awake and healthy and may stop the treatment session at any time simply by removing the nasal mask. The duration of the treatment is only 15 minutes, and the subjects will be monitored during treatment by a member of the study team.

This is an investigational study which does not guarantee any direct benefit to the subjects, but the proposed treatment may provide some relief of pain and symptoms from acute migraine. In the near term, this study may show the benefit of using a new device, the CoolStat, in a clinical setting, for treating migraine pain and associated symptoms using only a flow of dry, ambient air. In the longer term, this study could also lead to the development of a small, portable device that can be self-administer directly by the migraine sufferer in a non-clinical setting, such as at home or at work. These potential benefits are considered to outweigh the minimal risk associated with participation in this study.

Subjects will be advised of the potential risks and benefits associated with this study in the IRB approved ICF.

## 3 OBJECTIVES AND ENDPOINTS

OBJECTIVES	ENDPOINTS	JUSTIFICATION FOR ENDPOINTS
Primary		
To evaluate the safety, tolerability and optimal dose of the CoolStat for acute treatment of migraine	
 
• Safety of the CoolStat device measured by incidence of adverse events
 
• Tolerability of the CoolStat device by percent of subjects who fail to complete the full treatment session
 
• Pain relief at 2 hours post treatment
 
	Validated in several other acute migraine treatment device studies.
Secondary		

To assess the efficacy of CoolStat, by way of reduction in severity of reported pain and other symptoms post treatment compared to baseline.
 
To confirm the sham and the blinding procedures
 
To determine the treatment effect size to use in future sample size calculations for a pivotal randomized trial.
	
 
• Pain relief immediately post treatment and at 24 hours post treatment.
 
• Pain freedom immediately, 2 hours, and 24 hours post treatment.
 
• Relief of migraine associated symptoms (nausea/vomiting, photophobia, phonophobia) immediately, 2 hours, and 24 hours post treatment.
 
	Validated in several other acute migraine treatment device studies.

OBJECTIVES	ENDPOINTS	JUSTIFICATION FOR ENDPOINTS
	
 
• Freedom from migraine associated symptoms (nausea/vomiting, photophobia, phonophobia) immediately, 2 hours, and 24 hours post treatment.
 
• Use of rescue medication between 2 and 24 hours.
 
• % of subjects who believe they received active treatment in each arm.
 
	

## 4 STUDY DESIGN

### 4.1 OVERALL DESIGN

This is a prospective, multi-center randomized, double-blind, sham controlled trial. It is hypothesized that transnasal evaporative cooling induced by the CoolStat using only ambient temperature, dry air will reduce the pain and other symptoms of migraine headaches during an acute episode.

There will be an active treatment group and a sham group. There will be a 1:1 ratio across groups, stratified by gender.

- Group I (active treatment 1): 18 LPM, dehumidified air, 15 minutes total
- Group II (active treatment 2): 24 LPM, dehumidified air, 15 minutes total
- Sham Group: 6 LPM, ambient air administered via CoolStat, 15 minutes total

Subjects will complete a short screening visit (0-60 days prior to treatment session), followed by a 24 hour study intervention and follow up period (15 minute treatment session, 2 hour monitoring period, 2 hour follow up questionnaire, and 24 hour follow up interview).

To minimize bias, both patient and the outcomes assessor will be blind to the treatment group. In addition, subjects will only be randomized and treated one time to eliminate within-subject bias.

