## 5.4 STRATEGIES FOR RECRUITMENT AND RETENTION

100 women and men of any race or ethnicity will be recruited for participation in this study from the patient population of participating headache clinics. Subjects must have had a diagnosis of migraine for at least one year and meet the specified eligibility criteria. If the patient is deemed eligible based on their medical history, he or she will be approached by the PI or his/her designee to discuss the study and the patient's potential enrollment. Up to 100 subjects may be consented in this study to account for screen failures (patients who consent to participate but do not return to the clinic with a qualifying migraine/are not randomized within the 60 day enrollment period). Up to 75 subjects will be randomized to a treatment group.

It is anticipated that approximately 80% of our sample population will be women, based on the fact that migraine disproportionately affects women. Pregnant women will not be included in this study. We anticipate 25% of our sample population to be in minority groups based on demographic data from our feasibility prototype study. No races or ethnicities will be excluded.

Although we are estimating participation in this study across race, gender and ethnicity as noted above, we will not be specifically controlling or limiting subject participation based on these factors.

Two options are available to recruit patients:

- Eligible patients can be recruited during a standard care visit if they are experiencing a migraine attack and meet the inclusion and exclusion criteria.
- Patients can also be screened beforehand (having been informed about the study at a standard visit or via advertisement), and arrange for an on-demand appointment in the future when they are experiencing an attack.

Subjects will receive study information and consent documents by qualified study personnel, and must sign these documents before study procedures are initiated. Then the investigator will verify that the patient meets all inclusion criteria and none of the exclusion criteria. If this is the case, the subject will be required to provide a value on an 4-point scale (0 = no pain, 3 = maximum pain) of the current pain associated with their migraine. The patient will then be randomized to either the high flow treatment group, low flow treatment group, or the sham group.

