### 6.1.3 DOSING AND ADMINISTRATION

There will be two active treatment doses and one sham dose evaluated in this study: a high flow (24 LPM) dry air, a low flow (18 LPM) dry air, and the sham flow (6 LPM) of ambient air. All treatment arms will be administered through blinded, pre-set settings on the CoolStat device. Study personnel will be provided an input number, e.g., 1-9 (to put in the CoolStat user screen) that correlates to the two active treatment arms as well as the sham arm. Redundant numbers are used to help protect the blinding process. When the CoolStat is turned on, it displays a series of user-friendly set up instructions on its display screen. The final step in the startup process involves inputting the ‘input number’, which will be done for each subject.

A randomization process will be used with the proposed study to assign the numerical input value and desiccant cartridge selection (A, B or C) for each subject at each site. We have arranged to use MedNet to support this work, including their cloud-based randomization tool. For example, when a particular study site receives a new subject, study personnel will log on to the MedNet database, which will then provide both a device numerical input value and a cartridge designation based on a preset randomly generated list for this study. For example, the study inputs may be 4C, or 5A or 9B, which would correspond to a high therapy arm, a low therapy arm and a sham arm, respectively. This will ensure that the treatment is assigned randomly to each subject and there will be no risk of the device being pre-programmed to the incorrect flow rate (i.e. from a prior subject).

More detail on the device startup process can be found in the Operator’s Manual and CoolStat QuickStart Guide.

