## 6.3 MEASURES TO MINIMIZE BIAS: RANDOMIZATION AND BLINDING

Subjects will be randomly assigned to one of the three study groups. Investigational devices will be programmed in a 1:1:1 ratio in order to achieve the desired ratio between the active and control groups.

Subjects will be blinded to treatment assignment until the completion of the study. All efforts will be made to keep the subject blinded during the study treatment and during the follow up assessments, including the 24 hour follow up interview.

To minimize bias, both the subject the outcomes assessor(s) will be blind to the treatment group. In addition, subjects will only be randomized and treated one time to eliminate within-subject bias. The device will operate in Blind mode for this study, in which the different flow settings are coded to a set of nine numbers. The randomization tool within the MedNet electronic data capture (EDC) will allocate each subject a coded flow number. In addition, the ‘used’ desiccant cartridges will look and be packaged in exactly the same way as the ‘fresh’ cartridges. The foil packaging will be marked with a set of three letters, and the randomization tool will also allocate each subject to a desiccant cartridge lot via these letters.

Data are to remain blinded per protocol throughout the study. However, unblinding of subjects by the study monitor, data manager and/or statisticians may occur in the event of a SAE that is deemed related to the study intervention. If time permits, the Investigator should make every attempt to contact the Sponsor and/or Medical Monitor before unblinding any subjects’ treatment. The Investigator may conduct emergency unblinding if necessary using the MedNet data capture system. The Investigator will have a one-time view of the treatment arm for one patient in such a situation, and will not be unblinded to the treatment arms for other any subjects.

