#### 9.4.2 ANALYSIS OF THE PRIMARY EFFICACY ENDPOINT(S)

Both primary efficacy endpoints are scored categorically (Grade 0: no pain, Grade 1: mild pain, Grade 2: moderate pain, Grade 3 severe pain).

These categorical data will be summarized by absolute (n) and relative (%) frequency tables.

For categorical variables/proportions, we will perform Kruskal-Wallis test (the nonparametric equivalent of the ANOVA) to determine if there is a difference across the three study groups.

If there is a difference, then the Mann-Whitney test will be performed to compare the groups to each other to determine where the difference lies. We will correct for multiple comparisons using Bonferroni correction. The multiple imputation method will be used as the primary method for handling missing data in this study.

---

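### Gender stratification is stated only in section 4.1: 6.1.3 and 6.3 do not repeat it and the primary tests in 9.4.2 ignore it (low priority).

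*Combined protocol and SAP*

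**What the plan says.** Section 4.1 makes gender a stratification factor: "There will be a 1:1 ratio across groups, stratified by gender". No other section mentions it.

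- **6.3** says "Subjects will be randomly assigned to one of the three study groups" and "Investigational devices will be programmed in a 1:1:1 ratio in order to achieve the desired ratio between the active and control groups". It names no stratum and no block structure.
- **6.1.3** says the MedNet tool issues a device number and a cartridge letter "based on a preset randomly generated list for this study". It neither mentions nor excludes strata.
- **9.4.2** says "we will perform Kruskal-Wallis test (the nonparametric equivalent of the ANOVA) to determine if there is a difference across the three study groups", followed by pairwise Mann-Whitney tests with a Bonferroni correction. Neither test has a stratum or covariate. Section 9.4.3 applies the same methods to the secondary endpoints.
- **5.4** expects about 80% women and adds "we will not be specifically controlling or limiting subject participation based on these factors".

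**The concern.** A stratification factor belongs in three places: the design statement, the specification from which the allocation list is built, and the analysis. Here it is in the first only. That leaves two possibilities.

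- **The list is stratified.** The analysis then discards a factor used in the allocation. When that factor predicts outcome, a test that ignores it overstates the variance of the treatment comparison and gives up some power.
- **The list is built from 6.1.3 and 6.3 without the stratum.** The few men can then fall unevenly across arms by chance, on the one factor the sponsor chose to balance.

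An allocation list cannot be repaired after enrolment. One secondary objective is an effect size for planning a pivotal trial, so the allocation and its matching analysis should be unambiguous.

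**Working it through.** **Inputs.** 75 randomized, 25 per arm (9.2). About 80% women (5.4), so 0.20 × 75 = 15 men, or 5 per arm if balanced. Two-sided alpha 0.05 (9.2). The Bonferroni level is taken as 0.05/3 = 0.0167, assuming all three pairs are compared. Planning rates are 56% and 8% (9.2).

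**The plan's own figure.** The 17 per group in 9.2 reproduces with Fisher's exact test: power is 0.813 at 17 and 0.774 at 16. Gender plays no part in it.

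**If the stratum is dropped.** Suppose 15 men fall at random among three arms of 25. The probability of counts (a, b, c) with a + b + c = 15 is C(25,a)·C(25,b)·C(25,c) / C(75,15). Summing over all such counts:

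- largest minus smallest arm at least 4 men: 0.425
- largest minus smallest arm at least 5 men: 0.270
- two given arms at least 4 men apart: 0.219

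A 4-man difference between two arms shifts the expected difference in response by (4/25) × (rate in women − rate in men). Suppose 50% response overall and 20% men. At gender odds ratio 2 the rates are 53.4% and 36.4%, so the shift is 0.16 × 17.0 = 2.7 points. At odds ratio 5 they are 57.2% and 21.1%, so it is 0.16 × 36.1 = 5.8 points. The standard error of the difference is √(2 × 0.5 × 0.5 / 25) = 14 points.

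**If the stratum is kept but ignored.** I compared one active arm with sham, with 5 men and 20 women in each, on relief yes/no. Pearson's test stands in for the unstratified test and Cochran-Mantel-Haenszel for the stratified one. Power is summed exactly over all 6 × 21 × 6 × 21 = 15,876 outcomes. The gender odds ratio is assumed, as are the rates other than 56% and 8%.

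| Active vs sham | Gender odds ratio | Alpha 0.05: unstratified / stratified | Alpha 0.05/3: unstratified / stratified |
|---|---|---|---|
| 56% vs 8% | 1 | 0.9800 / 0.9777 | 0.9384 / 0.9335 |
| 56% vs 8% | 5 | 0.9826 / 0.9834 | 0.9440 / 0.9488 |
| 56% vs 25% | 1 | 0.6540 / 0.6350 | 0.4352 / 0.4297 |
| 56% vs 25% | 5 | 0.6589 / 0.6577 | 0.4314 / 0.4595 |
| 65% vs 30% | 1 | 0.7548 / 0.7186 | 0.5398 / 0.5399 |
| 65% vs 30% | 5 | 0.7631 / 0.7585 | 0.5401 / 0.5700 |

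In the table, stratifying changes power by −3.6 to +0.1 points at 0.05 and by −0.5 to +3.0 points at 0.05/3. I then ran a wider grid: active 40% to 85%, sham 10% to 55%, at least 25 points apart. The largest gain is 3.8 points (75% vs 40%, odds ratio 5, alpha 0.05/3: 0.549 to 0.587). With no gender effect, the largest loss is 1.6 points at 0.05/3 and 4.4 points at 0.05.

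**Type I error.** With 30% response in both arms and a gender odds ratio of 5, the unstratified test rejects at 0.048 and the stratified at 0.050 (nominal 0.05). At nominal 0.0167 the figures are 0.0137 and 0.0158. So the unstratified test is slightly conservative when gender matters. With no gender effect it rejects at 0.054 (30% in both arms) or 0.065 (50%), against 0.050 and 0.053 stratified. Much of the apparent power loss at 0.05 is therefore discreteness in the unstratified test.

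**The case against.** **Silence is not a statement.** A gender-stratified list is also preset, randomly generated and 1:1:1. No section says which text governs the MedNet build, and 4.1 is as much part of the protocol as 6.3. A reader might infer that 6.1.3 and 6.3 specify an unstratified list and so contradict 4.1. They do not; they omit the stratum. This stands, and it limits the point to what may happen to the list.

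**Section 5.4 looks like a conflict but is not.** A reader might take its sentence on not controlling participation by gender as a denial of stratification. It concerns who enrols, not how enrolled subjects are allocated.

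**The gain may not exist.** Nothing in the documents shows that gender predicts relief, and with about 5 men per arm a stratified test can lose a little power. This stands. The loss of up to about 4 points at 0.05 is largely the discreteness shown above. At the planned Bonferroni level it is under 1 point in the tabulated settings and 1.6 points at worst in the wider grid.

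**The 42% counts men, not harm.** This stands too. The shift from a 4-man imbalance is small beside a standard error of about 14 points, and the error rate of the test already allows for chance imbalance.

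**Conclusion.** The point holds as a low-priority mismatch between the stated allocation and the planned analysis. The gender stratum is in 4.1 only, and the tests in 9.4.2 ignore it.

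A reader might infer that the planned tests are invalid, or that 25 per arm is undermined. Neither follows. Ignoring a prognostic stratum makes the test slightly conservative, and the sample size in 9.2 does not depend on gender.

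Using the stratum is worth at most about 4 points of power, and only under a strong assumed gender effect (odds ratio 5). With no gender effect there is a small loss. If the stratum is lost from the list, visible imbalance in men is likely enough to matter for presentation: 42% for a spread of 4 or more across three arms, and 22% for two given arms.

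These figures assume 15 men among 75, arms of exactly 25, yes/no relief in place of the four-grade scale, and three pairwise comparisons. The gender odds ratio is not in the documents.

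**What to change.** 1. **9.4.2.** Replace the planned tests with their gender-stratified versions, matched to the single outcome the sponsor names as primary. Section 9.1 frames that outcome as a proportion with relief, while 9.4.2 describes a four-grade score. If it is the pain grade, use a stratified rank test of van Elteren type, overall and pairwise. If it is relief yes/no, use Cochran-Mantel-Haenszel, overall and pairwise. Name one, so that the choice is not left open until the data are seen.
2. **6.1.3 and 6.3.** State that the MedNet list is 1:1:1 within gender, with block details kept from the sites, and check the system configuration against this.
3. **4.1.** While editing, reconcile the 1:1 wording and the reference to a single active group with the three arms listed there and the 1:1:1 in 6.3.

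The cost is a few sentences and one configuration check before the data are unblinded. Demographics are already recorded at screening (1.3), so no new data are needed. The downside is the small possible power loss shown above if gender turns out not to matter.
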